2.1. Methylation Subsystem

Dysregulation of DNA methylation patterns plays a critical role in tumorigenesis in many cancers (Kay et al., 1995). It is well established that tumors shed DNA into the blood via a variety of

This document contains confidential, proprietary information and may not be reproduced or disclosed in whole or in part without written authorization from Freenome Holdings, Inc

		Approval Status	Approved
		Effective Date	5-Jan-2024
Document Number	PL-00052	Current Revision	5
Document Title	Clinical Validation of Freenome's Methylation Blood Test for the Early Detection...		
Document Category	Plan		

active and passive processes (Tsang & Lo, 2006), and detection of aberrant methylation patterns among circulating tumor DNA (ctDNA) can be used to identify the presence of tumors non-invasively (Yamaguchi et al., 2003). [REDACTED]

[REDACTED]

[REDACTED]

[REDACTED] This panel was then used in case-control biomarker discovery studies conducted in-house with prospectively collected plasma samples from non-ACN (including non-advanced adenomas), AA and CRC patient groups. Through multiple rounds of statistical and machine learning classifier analysis, we identified a final panel that enables accurate classification of ACN from plasma-isolated cfDNA. Specifically, the methylation component of FMBT-CRC determines if a patient sample contains cfDNA methylated at CpG (a cytosine followed by a guanine) sites. [REDACTED]

[REDACTED]

[REDACTED] A fragment corresponds to a single cfDNA molecule in the source sample. [REDACTED]

[REDACTED]

[REDACTED]

[REDACTED]

[REDACTED]	[REDACTED]	[REDACTED]
[REDACTED]	[REDACTED]	[REDACTED]

[figure not shown]
This document contains confidential, proprietary information and may not be reproduced or disclosed in whole or in part without written authorization from Freenome Holdings, Inc

		Approval Status	Approved
		Effective Date	5-Jan-2024
Document Number	PL-00052	Current Revision	5
Document Title	Clinical Validation of Freenome's Methylation Blood Test for the Early Detection...		
Document Category	Plan		

[REDACTED]	[REDACTED]	[REDACTED]

This document contains confidential, proprietary information and may not be reproduced or disclosed in whole or in part without written authorization from Freenome Holdings, Inc

		Approval Status	Approved
		Effective Date	5-Jan-2024
Document Number	PL-00052	Current Revision	5
Document Title	Clinical Validation of Freenome's Methylation Blood Test for the Early Detection...		
Document Category	Plan		

2.2. Subsystem Controls

The methylation subsystem utilize a number of controls as part of the workflow. These controls are set forth below (Table 2).

Table 2 - Methylation Subsystem Controls

Control	Description
Positive Control (PC)	Sheared genomic DNA from a cell line with a known HMF rate similar to early-stage CRC samples.
Negative Control (NC)	Sheared genomic DNA from a cell line known to lack hypermethylation in CRC biomarker regions that is PCR amplified and size selected.
Extraction Control (EC)	A control used to assess cfDNA extraction success. The composition is identical to the PC.
No Template Control (NTC)	Non-template control or no-template control; an assay control that does not contain a nucleic acid template necessary to generate the assay product through an assay process; used to detect nucleic acid contamination in assay reagents, consumables, or instruments.

This document contains confidential, proprietary information and may not be reproduced or disclosed in whole or in part without written authorization from Freenome Holdings, Inc

		Approval Status	Approved
		Effective Date	5-Jan-2024
Document Number	PL-00052	Current Revision	5
Document Title	Clinical Validation of Freenome's Methylation Blood Test for the Early Detection...		
Document Category	Plan		

2.3. FRNM Software Platform (SP)

The molecular data from the laboratory processing of the blood samples are analyzed by the FRNM-SP software. FRNM-SP is proprietary cloud-based software that includes: Analytical pre-processing (e.g. sequence alignment and quality control) of input data derived from laboratory processing of the sample, computational “featurization,” which transforms pre-processed inputs into the quantitative features required by a trained ML model, and application of the trained ML classification algorithm to the featurized inputs.

Freenome’s computational pipeline and model is shown below in Figure 2. This pipeline launches when it receives a notice that the data from the sample processing is available. The methylation workflow inputs to FMBT-SP are a BCL file from an [REDACTED] sequencer, and a samplesheet from SLIMS that provides metadata about the BCL file.

[figure not shown]

Figure 2 - Freenome FMBT-CRC-Methylation computational pipeline

The FMBT-CRC Methylation classifier workflow compares the methylation score directly to a methylation-specific threshold to determine the diagnostic result, positive or negative. This is shown in Figure 3.

This document contains confidential, proprietary information and may not be reproduced or disclosed in whole or in part without written authorization from Freenome Holdings, Inc

		Approval Status	Approved
		Effective Date	5-Jan-2024
Document Number	PL-00052	Current Revision	5
Document Title	Clinical Validation of Freenome's Methylation Blood Test for the Early Detection...		
Document Category	Plan		

[figure not shown]

Figure 3 - Freenome FMBT-CRC-Methylation Classifier Workflow

3. FMBT-CRC Classification Model

3.1. Detection of ACN

As noted in Section 2.3, the FMBT-CRC-Methylation Classification Model generates a qualitative result by incorporating inputs from the methylation subsystem. These inputs are analyzed by an artificial intelligence and machine learning (AI/ML)-enabled classification model that combines the methylation values from all loci with a non-linear integrative function to generate a score and compare it to a threshold learned during model training, yielding a qualitative result. Scores at or above the threshold result in a positive call. Scores below the threshold result in a negative call.

3.2. CpG Methylation Score

The summarized value for methylation signal is based on counting HMFs identified in the cfDNA NGS data. The model first aligns fragment sequences to the human reference genome in order to associate each fragment with a predetermined genomic region. Genomic regions are further subdivided into sequential 100 base pair (bp) bins, to address the high degree of CpG density inhomogeneity along the genome. In model training, for each bin i , a large number of fragments derived from healthy donor samples are compared to fragments derived from ACN patient samples, and a per-bin HMF methylated CpG threshold (s_i) is learned. Fragments intersecting bin i and with a methylated CpG count at or above the s_i threshold are deemed to be

This document contains confidential, proprietary information and may not be reproduced or disclosed in whole or in part without written authorization from Freenome Holdings, Inc

		Approval Status	Approved
		Effective Date	5-Jan-2024
Document Number	PL-00052	Current Revision	5
Document Title	Clinical Validation of Freenome's Methylation Blood Test for the Early Detection...		
Document Category	Plan		

hypermethylated. Once the model has assessed all available fragments and identified any HMFs, it produces a total HMF count (H):

$$H = \sum_i \#\{\text{HMFs in bin } i\}.$$

[figure not shown]
Because the number of eligible fragments varies from sample to sample due to differences in cfDNA extraction and capture behavior, the model also computes the number of eligible fragments per bin: those intersecting the bin and with at least s_i CpGs (either methylated or unmethylated). The total eligible fragment (E) count is computed as:

$$E = \sum_i \#\{\text{eligible fragments in bin } i\}.$$

Finally, the HMF ratio is defined as $R = H/E$. The HMF ratio provides the single summarized value for CpG methylation signal.

3.3. Model ensemble

Because the FMBT-CRC-Methylation classification model, like most ML models, requires hyperparameter optimization, cross-validation was used in model training. Specifically, the full training data set was iteratively split into training, tuning, and test folds. (Tuning folds are used for hyperparameter selection, and test folds provide provisional model performance estimates to guide the development process.)

3.4. Classification

This document contains confidential, proprietary information and may not be reproduced or disclosed in whole or in part without written authorization from Freenome Holdings, Inc

		Approval Status	Approved
		Effective Date	5-Jan-2024
Document Number	PL-00052	Current Revision	5
Document Title	Clinical Validation of Freenome's Methylation Blood Test for the Early Detection...		
Document Category	Plan		

To enable classification, the FMBT-CRC-Methylation ML classification model learned a classification threshold (t) based on behavior in negative samples during training and selected to yield a desired specificity. If $S \geq t$, the classifier returns a positive call.

4. Scope of the Analyses

This statistical analysis plan describes the methods to be used for clinical validation analysis of biological samples and data collected under Freenome Protocol FRNM-004, *PREEEMPT CRC: Prevention of Colorectal Cancer Through Multiomics Blood Testing*, Version 3.0. This statistical analysis plan should be read in conjunction with the PREEEMPT CRC study protocol, Version 3.0.

PREEEMPT CRC was an observational, prospective, multi-center study including participation from over 130 different clinical sites widely distributed across the U.S., and one site outside the U.S., the Cleveland Clinic Abu Dhabi. This Institutional Review Board-approved study enrolled asymptomatic, average-risk subjects who met eligibility criteria and provided informed consent.

Ensuring diversity in the participating patient population was a priority throughout this study. As part of this effort, the Sponsor focused on engagement with sites that contributed to the ethnic/racial as well as socioeconomic diversity of the study population. These sites included the participation of the Morehouse School of Medicine in Atlanta, Georgia (which has since presented in collaboration with the Sponsor on some of their experiences (Mills et al, 2022; Mills et al., 2021)), the University of Chicago Institute for Population and Precision Health in Chicago, Illinois, the Cleveland Clinic Abu Dhabi in the United Arab Emirates, as well as sites comprehensively representing regions across the U.S.

PREEEMPT CRC began enrollment in May 2020, two months after the start of the COVID-19 pandemic. As such, the impact of the pandemic was closely monitored during execution of the study by both the Sponsor and the independent Data Monitoring Committee (DMC). Several mitigations for the impact of COVID-19 were devised and integrated into study plans. These plans included the engagement of a virtual enrollment platform, Science 37, to increase outreach to potential subjects by extending and providing an alternative, virtual pathway for patient engagement. Subjects were also provided options to help facilitate participation in a remote setting, such as e-consenting and sample collection via mobile phlebotomy. These mitigations were implemented in a manner consistent with guidance provided by FDA (FDA, 2021).

This document contains confidential, proprietary information and may not be reproduced or disclosed in whole or in part without written authorization from Freenome Holdings, Inc

		Approval Status	Approved
		Effective Date	5-Jan-2024
Document Number	PL-00052	Current Revision	5
Document Title	Clinical Validation of Freenome's Methylation Blood Test for the Early Detection...		
Document Category	Plan		

Despite mitigations for COVID-19 as described above, during the early phase of the study, the pandemic had a profound impact on the healthcare system and the willingness of the general population to access health care for other than emergency conditions. This was especially true of patients with more advanced age and significant comorbidities who were understood to have higher risks of morbidity and mortality associated with COVID-19. The pandemic impact likely introduced shifts and biases in the set of individuals participating during this period which are unmeasurable and cannot be corrected for by statistical adjustment. As it is critical to maintain blinding to the diagnosis of CRC cases in this study, this issue will be addressed by pre-specifying an exclusion date coinciding with when the study was most impacted by COVID-19 (Fleming et al., 2020). By removing this earlier time interval, which has higher potential bias and confounders, the analysis population will better represent the IUP. The natural milestone of April 5, 2021 was used as the exclusion date, which corresponds to the execution of the protocol revision. The protocol revision helped further implement COVID-19 mitigations and the time period of the revision coincided with much of the U.S. opening up vaccination to all populations, thus easing restrictions on mobility and improved willingness to access healthcare (The American Journal of Managed Care, 2021). Therefore, enrollment on or after April 5, 2021 marked the beginning of a more representative population and will be used as the enrollment period for subjects included in this analysis, defined as the Enrolled* group.

The potential impacts that COVID-19 had on early study participation is supported by observed fluctuations in the epidemiological prevalence of CRC, which was originally assumed to be 0.5% during early study surveillance. The cause for these fluctuations is believed to reflect changes in both healthcare practice and patient behavior during the early months of the pandemic. At the kickoff of the PREEMPT DMC in July 2020, the DMC noted that the study might be impacted by the challenges for people to get access to CS due to the pandemic, resulting in underrepresentation of the breadth of comorbidities present in the IUP. Freenome continued to monitor screening rates throughout the study, and in order to assure blinding was maintained, developed a methodology to estimate CRC rates based on an approximate range of cases undergoing central pathology review at the time, a “bin” estimate, from which CRC rates could be periodically monitored. The assumed prevalence of CRC was amended in the protocol to 0.3% on April 5, 2021, which increased the enrollment target from 13,715 subjects to 25,000 subjects. As part of this amendment, the Sponsor also increased the number of study sites from 90 sites to approximately 120 sites, eventually reaching approximately 200 sites participating in the study. By the time of the next DMC meeting in July 2021, the Committee noted the study was progressing well and the rate of CRC was increasing. In March 2022, after assessing the latest metrics for the study, the DMC assessed that the necessary number of CRC cases had been reached and aligned on the decision to close enrollment for the study.

This document contains confidential, proprietary information and may not be reproduced or disclosed in whole or in part without written authorization from Freenome Holdings, Inc

		Approval Status	Approved
		Effective Date	5-Jan-2024
Document Number	PL-00052	Current Revision	5
Document Title	Clinical Validation of Freenome's Methylation Blood Test for the Early Detection...		
Document Category	Plan		

Another impact the pandemic had on the study was the extended storage of blood samples. The slower than expected initial enrollment and the increased enrollment target caused by the lower assumed CRC prevalence required the Sponsor to extend the enrollment period for the study. As a result, samples were stored considerably longer than originally planned. The PREEMPT CRC samples will begin processing around July 2023. Using the April 5, 2021 (inclusive) cutoff date for the analysis population reduces the real-time plasma stability data needed to 27 months. In order to include samples from date of first enrollment, in May 2020, real-time plasma stability data would be needed for 39 months.

The clinical validation of the FMBT-CRC will be based on PREEMPT CRC samples from participants enrolled on or after April 5, 2021, due to the fact that subjects enrolled prior to this date were less likely to represent the IUP and it would be unlikely that the unmeasured factors could be accounted for in analysis. This population, which enrolled after vaccines allowed improved access to healthcare, had a CRC incidence rate more in line with epidemiological predictions. Revised power calculations, using the revised enrollment window, show that the study is still overpowered for estimating the primary and secondary endpoints with a high degree of confidence.

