### 7.3.4 Additional Analyses

Additional analyses include, for example, analysis of distribution of cancers by age, biological sex, race, and ethnicity: Using a chi square or Fisher's exact test of the observed incidence of CRC (or CRC and AA) relative to the expectation from SEER incidence data will help assess the representativeness of the study population.

Direct rate standardization will be used to project the Sn and Sp (for CRC and AA) of Freenome's test to the general population, males, females and subjects  $\geq 65$  years of age.

The distribution and receiver operating characteristic (ROC) curves for Freenome's test score among the FAS subject group separately will be included. The AUC of each curve will be presented with its estimated 95% CI. For the same groups, the Sn and Sp of subject test scores will be presented over the range of scores, with Youden's J and number needed to misdiagnose one (NNMD) superimposed on the figure.

More details of analyses will be described in the SAP.

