8.4. Subgroup Analyses

Note: PREEMPT is not prospectively powered for subgroup analysis, nor is study alpha controlled for subgroup analysis. Reported analyses and p-values should be interpreted accordingly.

For subjects in the FAS, the condition prevalence (i.e. CRC, AA, Non-ACN) and clinical performance (unless otherwise noted, CRC sensitivity, AA sensitivity, and non-ACN specificity) of FMBT-CRC will be compared using Fisher-Freeman-Halton Exact tests for the following categorical variables (FDA 2017):

- Biological sex
- Race/ethnicity
- Categorical age brackets (note: for this analysis, a Cochrane-Armitage test for trend will be performed)
- Smoking status
- CS completion within 90 days vs. > 90 but \leq 120 days after blood collection
- For CRC, cancer stage
- For CRC, location (proximal, distal and rectal)
- For AA, sub-type (2.1-2.5)
- For AA, location (proximal, distal and rectal)
- For AA, index lesion size (\leq 5, 6-9, 10-19, 20-29, and \geq 30mm). (note: for this analysis, a Cochrane-Armitage test for trend will be performed)

The clinical performance of FMBT-CRC will also be analyzed via multivariate logistic regression (probability of a positive FMBT-CRC result as a function of listed variables) as follows:

This document contains confidential, proprietary information and may not be reproduced or disclosed in whole or in part without written authorization from Freenome Holdings, Inc

		Approval Status	Approved
		Effective Date	5-Jan-2024
Document Number	PL-00052	Current Revision	5
Document Title	Clinical Validation of Freenome's Methylation Blood Test for the Early Detection...		
Document Category	Plan		

- For NAA and AA (Categories 2-3), analysis of test positivity by index lesion size and location. The model will be repeated to also include age, biological sex, and race variables.
- For non-ACN, analysis of test positivity controlling for race, biological sex, and age.
- For CRC and AA (separately), analysis of test positivity, controlling for age, biological sex, race, index lesion size and lesion location.

Note: for multivariate logistic regression, Wald tests will be used to evaluate each factor for statistical significance, and age will be treated as a continuous factor.

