8.5. Additional Analyses

1. Descriptive statistics for medical history, concomitant medication, adverse events, summary of blood test accessioning, processing, and findings, and summary of colonoscopy findings.
2. Diagnostic yield.
3. Report percentage of results with invalid tests.
4. Subject demographics and analysis of test performance (Sn, Sp, PPV, NPV, PLR and NLR) homogeneity by sites stratified by Science 37 and non-Science 37 sites, and US vs non-US sites.
5. Analysis of test performance (Sn, Sp, PPV, NPV, PLR and NLR) for the following age-based USPSTF (2021) Grade groups:
 - 5.1. USPSTF Grade "A" (50-75)
 - 5.2. USPSTF Grade "A+C" (50-85)
 - 5.3. USPSTF Grade "B+A" (45-75)
 - 5.4. USPSTF Grade "B+A+C" (45-85)
6. Comparison of age and sex distributions to US estimates.
7. NPV and PPV using U.S. IUP prevalence.

This document contains confidential, proprietary information and may not be reproduced or disclosed in whole or in part without written authorization from Freenome Holdings, Inc

		Approval Status	Approved
		Effective Date	5-Jan-2024
Document Number	PL-00052	Current Revision	5
Document Title	Clinical Validation of Freenome's Methylation Blood Test for the Early Detection...		
Document Category	Plan		

8. Direct rate standardization will be used to project the sensitivity (Sn_{ACN} , Sn_{CRC} , and Sn_{AA}) and specificity ($Sp_{non-ACN}$) of FMBT-CRC to the general population based on age brackets and biological sex. Standardization will be repeated, projecting for condition prevalence (based on age brackets and sex) to the general population, prior to projecting the sensitivity and specificity to the general population.
9. Number needed to screen per disease-positive finding (CRC, Stage I to III CRC, AA).

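### SAP 8.5 compares with and projects to the U.S. on age and sex only; race and ethnicity belong in the comparison and in a sensitivity projection of specificity

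*SAP*

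**What the plan says.** - **Recruitment.** SAP Section 4 calls diversity a priority and states that "the Sponsor focused on engagement with sites that contributed to the ethnic/racial as well as socioeconomic diversity of the study population". It names two U.S. institutions and the Abu Dhabi site, and adds sites from across U.S. regions. It gives no target mix, no study shares and no U.S. shares.
- **External comparison.** SAP 8.5 item 6 reads "Comparison of age and sex distributions to US estimates". Race and ethnicity are absent.
- **Projection.** SAP 8.5 item 8 standardizes three sensitivities and Sp_non-ACN "to the general population based on age brackets and biological sex". A second version follows: "Standardization will be repeated, projecting for condition prevalence (based on age brackets and sex) to the general population".
- **Model for false positives.** SAP 8.4 lists "For non-ACN, analysis of test positivity controlling for race, biological sex, and age". The same section tests prevalence, sensitivity and non-ACN specificity across race/ethnicity categories.
- **Protocol check.** Protocol 7.3.4 plans an "analysis of distribution of cancers by age, biological sex, race, and ethnicity", in which observed incidence "relative to the expectation from SEER incidence data will help assess the representativeness of the study population". The SAP neither repeats this nor withdraws it. The SAP is to be read together with the protocol, but protocol Section 7 gives the SAP precedence where the two differ.
- **Other uses of race/ethnicity.** It is tabulated at baseline for four populations (SAP 8.3) and compared descriptively between excluded subjects and the FAS (SAP 8.7).

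**The concern.** The SAP treats three factors as possible drivers of a false-positive result: race, sex and age. Two of them enter the U.S. comparison and the projection. The third, which bears on how sites were engaged, does not. Direct standardization removes imbalance only in the factors it weights on, so any racial/ethnic imbalance within age-sex cells passes straight into the projected specificity.

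The other planned analyses do not close this gap. The tables and tests in 8.3 and 8.4 would show the study mix and whether specificity varies by race/ethnicity, but they do not set that mix against the U.S. mix. The comparison in 8.7 is internal to the study. Item 4 of 8.5 splits U.S. from non-U.S. sites, which is a different question. If 8.4 did show a difference, no pre-specified step would carry it into the projected figure, and a correction added afterwards would be data-driven. At stake is the accuracy of a figure offered for the general population, not the study's success criterion.

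**Working it through.** **The plan's own specificity figure.** SAP 7.2 gives 454 non-ACN subjects, at least 401 negative, a lower bound of 85.0% and at least 90% power at a true specificity of 90.2%. The Wilson lower bound is 85.05% for 401/454 and 84.80% for 400/454, so 401 is the critical value. The exact one-sided error is 0.0247 and the power 92.0%. The figure reproduces. It concerns observed FAS data, with no standardization.

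**Form of the residual bias.** Take one group whose false-positive rate exceeds that of the rest by *d*, with study share *s* and U.S. share *u*, each constant across age-sex cells. With cell weights *w* and specificity *b* in the rest:

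- standardized on age and sex: Σ*w*(*b* − *s·d*)
- standardized on age, sex and race/ethnicity: Σ*w*(*b* − *u·d*)
- difference: −(*s* − *u*)·*d*

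The size is share difference × false-positive difference. The sign depends on whether the group is over- or under-represented, which the documents do not reveal.

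**Inputs.** The documents supply neither the shares nor specificity by race/ethnicity. Assumed ranges: share difference 5–15 points, false-positive difference 2–5 points.

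| Share difference | False-positive difference | Bias in projected Sp |
|---|---|---|
| 5 points | 2 points | 0.05 × 2 = 0.10 points |
| 10 points | 3 points | 0.10 × 3 = 0.30 points |
| 15 points | 5 points | 0.15 × 5 = 0.75 points |
| any | 0 | 0 |

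**Scale of sampling error.** From SAP Section 7, FAS 19,000, CRC prevalence 0.30%, and AA prevalence 34.265/(34.265 + 436.699) = 7.28%.

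- Non-ACN subjects: 19,000 × (1 − 0.0030 − 0.0728) ≈ 17,560
- Standard error at 90.2%: √(0.902 × 0.098 / 17,560) = 0.224 points
- 95% half-width: 1.96 × 0.224 = 0.44 points

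**Break-even.** The false-positive difference at which the bias equals 0.44 points is 0.44/0.05 = 8.8 points for a 5-point share difference, 0.44/0.10 = 4.4 for 10 points and 0.44/0.15 = 2.9 for 15 points. Only the upper part of the assumed grid exceeds sampling error.

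**What 8.4 would detect.** For a group making up 10% of non-ACN subjects, a two-sided 0.05 test has approximate power of 27% for a 1-point specificity difference, 74% for 2 points and over 99% for 5 points.

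**The case against.** The strongest reply has four parts.

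1. *The size is assumed throughout.* True. Two of the three nonzero worked values lie below 0.44 points, and no difference in specificity means no bias.
2. *The 0.44 benchmark is not an interval in the SAP.* Also true. It is an unweighted planning figure, and weighting widens it. If 70% of the FAS is aged 65 or over and 30–45% of the target population is (an assumption), two-stratum weighting multiplies the variance by *p*²/0.7 + (1 − *p*)²/0.3. That is 1.76 at *p* = 0.30 and 1.30 at *p* = 0.45, for a half-width of about 0.58 to 0.50. So one cannot say that the SAP's interval is too narrow by a known amount.
3. *The analyses in 8.4 already show whether race/ethnicity matters.* They would show the larger differences, and a reader could then gauge the effect of reweighting. They neither set the mix against the U.S. nor correct the projection.
4. *The protocol never planned to weight on race, and the SAP's revision log ties the standardization wording to commitments made to FDA.* Both stand. They are reasons to leave the age-sex version untouched and add to it.

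A reader might also infer that site selection moved the racial/ethnic mix away from the U.S. mix. SAP Section 4 does not say so: sites were engaged to contribute to diversity, which could have brought the mix closer. Nor does the synopsis's description of a representative sample claim the U.S. racial mix; it refers to average-risk people having screening colonoscopy at the study's sites.

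**Conclusion.** The omission in SAP 8.5 items 6 and 8 is real and worth correcting; its effect is conditional. Projected Sp_non-ACN is biased only if specificity differs by race/ethnicity and the study mix differs from the U.S. mix within age-sex cells. Direction and size are unknown. Under the assumed inputs the bias is 0.10–0.75 points, above the approximate unweighted half-width of 0.44 points only toward the upper end.

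Two stronger conclusions are not supported. One is that representativeness by race and ethnicity goes wholly unchecked: the SEER comparison in protocol 7.3.4 covers it in part and has not been withdrawn, although it concerns cancer incidence rather than population mix and its standing under the SAP is unclear. The other is that the study's success is at risk: SAP 6.3 applies the 85.0% specificity criterion to observed FAS data, and item 8 is an additional analysis that enters no acceptance criterion.

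**What to change.** 1. In SAP 8.5 item 6, add race and ethnicity to the comparison with U.S. estimates, and name the reference source and categories.
2. In item 8, pre-specify a sensitivity projection of Sp_non-ACN with race/ethnicity as a raking margin beside the age-by-sex margin, reported next to the unchanged age-sex version. Keep Sn_CRC on age and sex, since the plan requires a minimum of only 56 CRC cases.
3. State whether the SEER comparison by race and ethnicity in protocol 7.3.4 is retained, and if so list it in 8.5.

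The study data are already collected and tabulated under 8.3. The cost is SAP wording, a U.S. reference distribution and one more weighted estimate, whose interval will be slightly wider because the weights vary more.
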